6.6.2 Replacement

Patients who have undergone a gadoterate-enhanced MRI but have no enhancing lesions identified will not be enrolled. Recruitment will, therefore, continue until at least 180 patients have completed both the gadoterate and gadobutrol studies.

6.7 Patient identification

The patient number is a 9-digit number consisting of:

Digits 1 to 5 = Unique center number

Digits 6 to 9 = Current patient number within the center

After patients have signed an informed consent form, they will be identified by a unique 9 digit patient identification number (PID). The PID will identify the patient throughout the study. The first 2 digits represent the country number, the second 3 digits represent the center number, and the third 4 digits represent a sequential number in the order in which the patient signed the informed consent at the study center. For example, the third patient enrolled at center number in the patient in the patient (14) would be PID

7. Treatments

7.1 Treatments to be administered

7.1.1 Gadobutrol

Gadobutrol injection (Gadovist/Gadavist) is the gadolinium complex of 10-[2,3-dihydroxy-1-(hydroxymethyl) propyl]-1,4,7,10-tetraazacyclododecane-1,4,7-triacetate (see Figure 7-1). This is a neutral chelated, racemic complex of the rare earth element gadolinium (Gd3+). Gadobutrol injection is a white to off-white, highly water soluble substance that is an injectable contrast medium for MRI. Gadobutrol is to be administered by IV injection.

Figure 7-1: Structural Formula of Gadobutrol

Molecular weight: 604.72 g/mol

26 MAR 2019 Version no. 2.0 Page: 21 of 60

Each milliliter of 1.0 molar gadobutrol injection (SH L 562 BB) contains 604.72 mg of pure gadobutrol, 0.513 mg calcium sodium butrol, 1.211 mg tromethamine, 0.1N hydrochloric acid and water for injection. Gadobutrol injection contains no antimicrobial preservative. For a description of the product characteristics, including pertinent physicochemical data, see the Investigator's Brochure.

7.1.2 Gadoterate treatment

The comparator contrast agent is gadoterate (Dotarem®/ ClariscanTM), which is approved for steady-state CNS imaging. (See www.guerbet.com for Dotarem package insert, GE Healthcare for Clariscan.)

7.2 Dosage and administration

Patients will receive a single dose of gadoterate at the approved dose, 0.1 mmol/kg BW (± 10 percent), via IV bolus administration using a power injector via a peripheral vein (the antecubital vein is preferred). Gadoterate will be injected at a rate of 2 mL/second followed by a 20-mL 0.9% saline flush at the same rate. If the patient is eligible for inclusion in the study, the patient will undergo a second contrast-enhanced MRI using a single dose of gadobutrol 0.075 mmol/kg BW via IV bolus administration using a power injector via a peripheral vein (the antecubital vein is preferred). Gadobutrol will be injected at a rate of 2 mL/second followed by a 20-mL 0.9% saline flush at the same rate.

The administration of gadoterate and gadobutrol is not randomized. During the 24-hour follow-up period after the gadoterate injection and during the 24-hour follow-up period after the gadobutrol injection, no other contrast agent should be given.

7.3 Identity of study treatment

Marketed drugs will be used for this study. If required at country level, the study drugs will be labeled according to the requirements of local law and legislation. Label text will be approved according to the sponsor's agreed procedures, and a copy of the labels will be made available to the study site upon request.

A complete record of batch numbers and expiry dates of all study treatment as well as the labels will be maintained in the sponsor's study file.

26 MAR 2019 Version no. 2.0 Page: 22 of 60

7.4 Blinding

The study is formally unblinded, however, all primary and most secondary efficacy endpoints (except for the open-label site investigator assessments) are blinded.

For the off-site blinded read, study images for each subject will be reviewed both unpaired and paired. The gadoterate and gadobutrol image sets from the same patient will be randomized. For the paired reading, the gadoterate and gadobutrol images will be shown randomly on either the right or left monitor.

Three experienced radiologists who are not involved with the conduct of the study, the evaluation of local study images at the site, and/or the recruitment of patients will be selected to perform the independent blinded image evaluations. Each blinded reading session will have sufficient separation (at least 2 weeks) between the unenhanced and combined unenhanced and enhanced MRI for each contrast agent to minimize recall bias (see Section 11.4). The images used for blinded evaluation sessions will not contain any information regarding the patient's privacy or clinical data. Information on study center, scanner manufacturer, or imaging times will not be provided to the blinded reviewers.

7.5 Drug logistics and accountability

The investigator will use the study drug only within the framework of this clinical study and in accordance with this study protocol. A record of the volume received will be recorded in the patients' eCRFs. Receipt and return of the study drugs must be properly documented on the forms provided by the sponsor.

7.6 Treatment compliance

The study drugs are administered by study center personnel who will record:

- Location of injection
- Study drug start date and time
- Study drug volume and rate of injection

The injection volume and rate of injection of the saline flush will be recorded in the eCRF.

8. Non-study therapy

8.1 Prior and concomitant therapy

Patients are not to receive any contrast agent within 24 hours prior to the first study MRI or 24 hours after the second study MRI. Patients may receive other concomitant medications, including sedation for the MRI examination, during the study. A patient's current medication regimen and/or any additional medication taken from baseline up to 24 hours after the second study MRI will be recorded in the eCRF.

26 MAR 2019 Version no. 2.0 Page: 23 of 60

8.2 Post-study therapy

Not applicable as this is a diagnostic-imaging study.

9. Procedures and variables

9.1 Tabular schedule of evaluations

Table 9-1 displays the schedule of evaluations and procedures for the study.

26 MAR 2019 Version no. 2.0 Page: 24 of 60

Table 9-1: Schedule of Study Events

		Stu	udy Period 1 ^a			Stud	dy Period 2 ^a		
Evaluation/Procedure	Baseline ^b	MR	I	Post Injection Phone Contact ^c	Baseline ^C	MR	I	Post Injection Phone Contact ^c	Final Diagnosis up to 30 days Phone call
Time Point	Up to 72 hours prior to the 1st MRI	Unenhanced	Enhanced	24h±4h	Within 24 h of the 2 nd MRI	Unenhanced	Enhanced	24h (±4 h)	Thorne can
Sign informed consent	Х								
Demographic data	X								
Medical/surgical history	X								
Baseline findings	X								
Referral diagnosis	X								
Previous/concomitant medications ^d	X			X	×			Х	
Weight ^e	χi				χi				
Urine pregnancy test ^f	χi								
Creatinine value ^g	X								
Gadoterate administration			Х						
Gadobutrol administration							Х		
Adverse event monitoring	X	Х	Х	Х	Х	Х	Х	Х	
Final clinical diagnosis up to 30 day post first MRI ^h									Х

Clinical Study Protocol

No. BAY No. 86-4875/ IMPACT no. 19773

26 MAR 2019 Version no. 2.0 Page: 25 of 60

Abbreviations: h = hour(s); immed = immediately; inj = injection; min = minutes

Notes:

- ^a A period of 24 h up to 15 days is required between the contrast agent injections;
- b Baseline for study period 1 is from after signing informed consent up to 72 hours for gadoterate administration;
- ^c Baseline for study period 2 is within the 24 h prior to administration of gadobutrol. At least 2 h is required between the 24-h follow-up evaluations from study period 1 and the baseline evaluations for study period 2. The patient will be contacted by phone after 24-hour (± 4 hours) after each contrast agent injection. The two MRI contrast agents will be separated by at least 24 hours, but not more than 15 days. Any TEAEs or TESAEs and/or concomitant medications reported during this period will be recorded in the eCRF.
- d All concomitant medication will be collected
- ^e Weight will be obtained at baseline and reconfirmed prior to the second MRI
- f Urine pregnancy test (if applicable) to be done at the site, according to the standard of the institution, and the results must be available prior to the gadoterate MRI.
- g Serum creatinine (eGFR value calculated using either MDRD or the CKD-EPI Creatinine Equation, 2009) derived up to 4 weeks prior to the first study MRI value and date obtained and method used needs to be recorded at Screening.
- ^h The final clinical diagnosis will be recorded by the investigator within 30 days of the first study MRI.
- i Within 1h of injection

26 MAR 2019 Version no. 2.0 Page: 26 of 60

9.2 Study periods

9.2.1 Baseline study period 1

Baseline is the up to 72 hour period from signing informed consent to administration of gadoterate (including saline flush).

Prior to administration of gadoterate the following will be performed: placement of IV injection line, urine pregnancy test (in women of child bearing potential the date and time of the pregnancy test sample and the result of the pregnancy test will be recorded in the eCRF). Results of the pregnancy test must be negative prior to the administration of any contrast agent.

The IV injection line will consist of a large bore indwelling catheter (at least 18 gauge) preferably placed in an antecubital vein. The location of the IV injection line must be documented in the eCRF.

9.2.2 Study period 1

The administration of gadoterate is study period 1 and the administration of the gadobutrol is study period 2.

The following procedures will be performed during study period 1:

- 1. An unenhanced MRI of the brain will be performed according to the standards of the institution.
- 2. The appropriate volume corresponding to 0.1 mmol/kg of gadoterate will be administered IV as a bolus injection at the rate of 2 mL/sec using a power injector via a peripheral vein (the antecubital vein is preferred) followed by a 20-mL 0.9% saline flush using a power injector at the same flow rate. The dose and volume of the contrast agent will be recorded.
- 3. AE monitoring will begin at baseline. All TEAEs will be monitored for 24 hours after the administration of each contrast agent. However, if no enhancing lesion is identified in the first imaging study, the patient will not be included in the safety database and only SAEs for that patient would be reported.
- 4. Conventional steady-state contrast-enhanced imaging with a T1w sequence according to the parameters listed in Section 10.2.1.2 will start 4 to 10 minutes following the injection of the contrast agent.
- 5. The patient will be asked about his/her physical condition. Any clinically significant changes in the patient's physical condition from the baseline values are to be recorded in the eCRF, and the TEAE section is to be completed accordingly.

26 MAR 2019 Version no. 2.0 Page: 27 of 60

According to the internal clock of the MR device, the date and start time of the first MR sequence, date and start time of the contrast injection and the end time of the complete MR examination will be recorded in the eCRF. Any deviation from the specified MRI procedures and the reason for it (scanner-related problem or patient-related problem) will be recorded in the eCRF.

9.2.3 Baseline study period 2

Any changes in concomitant diseases and concomitant medication will be recorded in the eCRF. The IV injection line will consist of a large bore indwelling catheter (at least 18 gauge) preferably placed in an antecubital vein. The location of the IV injection line must be documented in the eCRF.

9.2.4 Study period 2

The following procedures will be performed:

- 1. An unenhanced MRI will be performed exactly as done in Study Period 1.
- 2. The appropriate volume of 75% of the standard gadobutrol dose (0.075 mmol/kg BW) will be administered IV as a bolus injection at the rate of 2 mL/sec using a power injector via a peripheral vein (the antecubital vein is preferred) followed by a 20-mL 0.9% saline flush using a power injector at the same flow rate. The dose and volume of the contrast agent will be recorded.
- 3. Conventional steady-state contrast-enhanced imaging with a T1w sequence according to the parameters listed in Section 10.2.1.2 will start 4 to 10 minutes following the injection of the contrast agent.
- 4. The patient will be asked about his/her physical condition. Any clinically significant changes in the patient's physical condition from the baseline values are to be recorded in the eCRF, and the TEAE section is to be completed accordingly.

The date and start time of the first MR sequence, date and start time of the contrast injection and the end time of the complete MR examination will be recorded in the eCRF. Any deviation from the specified MRI procedures and the reason for it (scanner-related problem or patient-related problem) will be recorded in the eCRF.

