5.1 Design overview

This study is a Phase 4, multicenter, controlled, cross-over study with corresponding blinded image evaluations in male and female patients at least 18 years of age, who are referred for a contrast-enhanced MRI of the CNS based on a known or highly suspected lesion of the CNS.

Patients will undergo an unenhanced and contrast-enhanced MRI of the CNS using gadoterate at the standard dose of 0.1 mmol/kg BW. If the investigator does not identify an enhancing lesion of the CNS, then this patient will be considered a screening failure. If an enhancing lesion is identified, then the patient will undergo a second unenhanced and contrast-enhanced MRI of the CNS using gadobutrol at a dose of 0.075 mmol/kg BW.

Safety will be assessed from the first administration of gadoterate through 24 hours after the second administration of gadobutrol. Adverse events will be collected from the signing of informed consent through the end of the follow-up period. Serious adverse events (SAEs) will be followed through resolution. Patients who receive only the first MRI scan (considered screening failures) will be followed for SAEs only.

Gadobutrol will be administered at the dose of 0.075 mmol/kg body weight by single IV injection at a rate of 2 mL/sec, followed by 20-mL 0.9% saline flush at the same rate. Gadoterate will be administered at the approved standard dose of 0.1 mmol/kg body weight by single IV injection at 2 mL/sec, followed by 20-mL 0.9% saline flush at the same rate. The 2 injections will be separated by at least 24 hours, but not more than 15 days.

During the course of the study, 2 MRIs will be obtained from each patient as follows: before the administration of each of the contrast agent (unenhanced MRI) consisting of steady-state sequences (T1w, T2w, and FLAIR), following the gadoterate injection (gadoterate-enhanced MRI) consisting of steady-state sequences T1; and following the gadobutrol injection (gadobutrol-enhanced MRI) consisting of steady-state sequences (T1w).

The unenhanced MR image set, combined unenhanced and gadobutrol-enhanced MR image sets, and the unenhanced and combined unenhanced and gadoterate-enhanced MR image sets will be evaluated by 3 independent blinded readers. The blinded readers will also evaluate the

26 MAR 2019 Version no. 2.0 Page: 15 of 60

gadobutrol-enhanced T1w images compared to the gadoterate-enhanced T1w images in a paired read for image quality.

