9.2.5 Post-Injection phone contact

The patient must be contacted by phone after 24-hour (\pm 4 hours) after each contrast injection. The two MRI contrast agents will be separated by at least 24 hours, but not more than 15 days.

26 MAR 2019 Version no. 2.0 Page: 28 of 60

Any TEAEs or TESAEs and/or concomitant medications reported during this period will be recorded in the eCRF.

The end of Study Period 2 is after the 24 hour post injection AE follow-up phone call.

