10.4.1.3 Assessments and documentation of adverse events

The investigator must record on the respective CRF pages all adverse events occurring in the period between the signing of the informed consent and the end of the follow-up phase; all SAEs/TESAEs must be followed to resolution. After the end of the follow-up phase there is no requirement to actively collect TEAEs including deaths. The type of information that should be assessed and recorded by the investigator for each TEAE is listed in Section 10.4.1.2.

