The site must implement processes to ensure availability of all required source documentation. A source document checklist (not part of this protocol) will be used at the site to identify the source data for key data points collected and the monitor will work with the site to complete this.

It is the expectation of the sponsor that all data entered into the eCRF has source documentation available at the site.

Data recorded from screening failures

At minimum, the following data should be recorded in the CRF:

- Demographic information (patient number; year of birth / age; sex; if applicable race / ethnicity)
- Date of informed consent
- Relevant inclusion/exclusion criteria
- Reason for premature discontinuation
- Date of last visit.

These data will be transferred to the respective database.

For screening failures with a SAE / TESAE, the following data should be collected in the CRF in addition to the data specified above:

- All information related to the SAE / TESAE such as:
 - The SAE / TESAE itself
 - Concomitant medication
 - Medical history
 - Other information needed for SAE / TESAE complementary page

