3.1 Overall Design

This study is a Phase 4, multicenter, controlled, cross-over study with corresponding blinded image evaluations in male and female subjects at least 18 years of age, who are referred for a contrast-enhanced MRI of the CNS based on a known or highly suspected lesion of the CNS.

Subjects will undergo an unenhanced and contrast-enhanced MRI of the CNS using gadoterate at the standard dose of 0.1 mmol/kg BW. If the investigator does not identify an enhancing lesion of the CNS, then this subject will be considered a screening failure. If an enhancing lesion is identified, then the subject will undergo a second unenhanced and contrast-enhanced MRI of the CNS using gadobutrol at a dose of 0.075 mmol/kg BW.

Safety will be assessed from the first administration of gadoterate through 24 hours after the second administration of gadobutrol. Adverse events (AEs) will be collected from the signing of informed consent through the end of the follow-up period. Serious AEs (SAEs) will be followed through resolution. Subjects who receive only the first MRI scan (considered screening failures) will be followed for SAEs only.

Gadobutrol will be administered at the dose of 0.075 mmol/kg BW by single IV injection at a rate of 2 mL/sec, followed by 20-mL 0.9% saline flush at the same rate. Gadoterate will be administered at the approved standard dose of 0.1 mmol/kg BW by single IV injection at 2 mL/sec, followed by 20-mL 0.9% saline flush at the same rate. The 2 injections will be separated by at least 24 hours, but not more than 15 days.

During the course of the study, 2 MRIs will be obtained from each subject as follows: before the administration of each of the contrast agent (unenhanced MRI) consisting of steady-state sequences (T1w, T2 [transfersal relaxation time]-weighted [T2w], and Fluid Attenuated Inversion Recovery [FLAIR]), following the gadoterate injection (gadoterate-enhanced MRI) consisting of steady-state sequences of T1; and following the gadobutrol injection (gadobutrol-enhanced MRI) consisting of steady-state sequences (T1w).

The unenhanced magnetic resonance (MR) image set, combined unenhanced and gadobutrol-enhanced MR image sets, and the unenhanced and combined unenhanced and gadoterate-enhanced MR image sets will be evaluated by 3 independent blinded readers (BRs). The BRs will also evaluate the gadobutrol-enhanced T1w images compared to the gadoterate-enhanced T1w images in a paired read for image quality.

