6.4.2.1 Overview of AEs

The number and percentage of subjects experiencing AEs will be summarized. Overall summary tables will be provided for all AEs, TEAEs and pretreatment AEs with following categories:

- Any such AEs
- Drug-related AEs
- AEs related to procedures required by the protocol
- AEs by intensity (mild, moderate, severe)
- Drug-related AEs by intensity
- Serious AEs (SAEs)
- Drug-related SAEs
- SAEs related to procedures required by the protocol
- AEs leading to discontinuation of study drug
- SAEs leading to discontinuation of study drug
- AEs leading to death.

The overall summary table will also be presented on AEs of subjects only receiving gadoterate but not included in the SAF.

The number and percentage of subjects with TEAEs will be summarized for the following:

- TEAEs and treatment-emergent SAEs (TESAEs) by SOC and PT
- Drug-related TEAEs and TESAEs by SOC and PT
- Nonserious TEAE by SOC and PT
- TEAEs and TESAEs resulting in discontinuation of study drug by SOC and PT
- TEAEs and TESAEs by maximum intensity, SOC, and PT
- Drug-related TEAEs and TESAEs by maximum intensity, SOC, and PT
- TEAEs and TESAEs by worst outcome, SOC, and PT
- Drug-related TEAEs and TESAEs by worst outcome, SOC, and PT

Common TEAEs, TESAEs, drug-related TEAEs, and drug-related TESAEs with frequency $\geq 1\%$ by SOC and PT.

Tables will be sorted alphabetically by SOC and PT.

Subject listings of all AEs as well as subset listings of AEs leading to death and AEs resulting in discontinuation of study drug will be created.

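### SAP 6.4.2.1 plans the full AE overview for gadoterate-only patients outside the SAF, but the plan provides only for SAEs in them, so 6 of its 11 categories would be incompletely ascertained

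*Protocol*

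**What the plan says.** **The table.** After listing the categories of the overall AE summary, SAP 6.4.2.1 adds: "The overall summary table will also be presented on AEs of subjects only receiving gadoterate but not included in the SAF". It does not shorten the category list for this group. The list includes entries such as "AEs by intensity (mild, moderate, severe)".

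**Who is in it.** Under Protocol 6.6.2, patients whose gadoterate scan shows no enhancing lesion are not enrolled. SAP 5 defines the SAF as the enrolled subjects. These patients have therefore been dosed with gadoterate and are outside the SAF.

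**What is collected from them.** Three places give an SAE-only rule:
- Protocol 9.2.2 item 3, as an exception directly after the general rule on monitoring events for 24 hours: "if no enhancing lesion is identified in the first imaging study, the patient will not be included in the safety database and only SAEs" are reported for that patient.
- Protocol 5.1: "Patients who receive only the first MRI scan (considered screening failures) will be followed for SAEs only".
- SAP 3.1: "Subjects who receive only the first MRI scan (considered screening failures) will be followed for SAEs only".

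Protocol 12.1 sets minimum CRF data for screening failures, with no adverse event item among them, and then says: "For screening failures with a SAE / TESAE, the following data should be collected in the CRF in addition".

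**General recording rules.** Protocol 10.4.1.3 says: "The investigator must record on the respective CRF pages all adverse events occurring in the period between the signing of the informed consent"; this period closes when follow-up ends. Protocol 9.2.5, on the 24-hour call after each injection, says: "Any TEAEs or TESAEs and/or concomitant medications reported during this period will be recorded in the eCRF". Protocol 9.2.2 item 5 has clinically significant changes in the patient's condition recorded as events. None of the three repeats the exception.

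**The concern.** The planned table is wider than the data the plan undertakes to collect. SAP 3.1 and SAP 6.4.2.1 do not fit together, and the Protocol sides with SAP 3.1 in its specific wording but not in its general recording rules.

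A table with rows for any AE, for drug-related AEs and for AEs by intensity is normally read as a full account of events. If non-serious events were not sought, or were sought at some sites only, low counts in those rows reflect collection and not tolerability. Nothing in SAP 6.4.2.1 warns the reader. Describing the safety of both agents is a secondary objective, and these patients were exposed to one of them.

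**Working it through.** The documents give no figure to reproduce here. The check is a count of the SAP 6.4.2.1 categories, each classed by whether SAE-only collection is enough to fill it.

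| # | Category (paraphrased) | Filled from SAEs alone? |
|---|---|---|
| 1 | Any AE | No |
| 2 | Drug-related AE | No |
| 3 | Procedure-related AE | No |
| 4 | AE by intensity | No |
| 5 | Drug-related AE by intensity | No |
| 6 | SAE | Yes |
| 7 | Drug-related SAE | Yes |
| 8 | Procedure-related SAE | Yes |
| 9 | AE leading to discontinuation | No |
| 10 | SAE leading to discontinuation | Yes |
| 11 | AE leading to death | Yes |

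Category 11 counts as covered because death is seriousness criterion (a) in Protocol 10.4.1.1.

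- Filled from SAEs: categories 6, 7, 8, 10 and 11 = 5.
- Dependent on non-serious events: 11 − 5 = 6, and 6/11 = 55%.
- Counted as printed rows, the two intensity categories have three levels each. Total rows: 9 + 2 × 3 = 15. Rows dependent on non-serious events: 4 + 2 × 3 = 10.

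**Would the six be empty?** Not necessarily. Protocol 10.4.1.2 has intensity and causality assessed for every event, so SAEs alone would put entries into these rows. The general rules in Protocol 10.4.1.3, 9.2.5 and 9.2.2 item 5 may add some non-serious events. What the rows would lack is a defined level of ascertainment.

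**Which rule prevails?** Protocol 9.2.2 item 3 is worded as an exception to the general rule just before it, so the SAE-only reading is the more natural one. Under that reading the six categories are under-filled. If the general rules prevail instead, the table can be filled, but then Protocol 5.1, Protocol 9.2.2 item 3 and SAP 3.1 are wrong. The documents need reconciling either way.

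**Number of patients or events.** This cannot be derived. The documents give neither the share of dosed patients without an enhancing lesion nor any AE rate.

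**The case against.** The strongest reply is that non-serious events in these patients will be recorded anyway: the investigator must record all AEs, the 24-hour call follows each injection, and Protocol 12.1 sets a minimum and bars nothing. The point about 12.1 stands; it cannot be used as proof of SAE-only collection. The rest shows that some events may be captured. It does not show that they are captured systematically, given three statements to the contrary.

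It can also be said that this is a descriptive side table, that 55% is a share of table categories and not a measure of harm, and that cutting the table would hide events that were recorded. All of this stands. It limits the weight of the point and shapes the fix.

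A reader might go further and infer that the SAE-only sentence also reaches enrolled patients who stop after gadoterate, so that the SAF gadoterate column loses non-serious events. Taken alone, the sentence in Protocol 5.1 and SAP 3.1 does cover everyone with only a first scan. But the same sections define a screening failure earlier as a patient with no enhancing lesion, and Protocol 9.2.2 item 3 limits the rule to that group. SAF membership follows enrolment (Protocol 11.3.1.1, SAP 4.2, SAP 5), and Protocol 10.4.1.3 requires all AEs to be recorded. The dropout definition in Protocol 6.6.1 does leave unnamed an eligible patient who stops because of an AE, but that label does not decide who is analysed for safety.

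A reader might also infer from Protocol 10.4.1.4, which places most events within 30 minutes of administration, that early events would be entered and later ones lost. The documents do not say when the scan is read or how sites handle such entries, so this is conjecture.

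**Conclusion.** The mismatch between the table and the collection rule holds. Six of the 11 overview categories planned for gadoterate-only patients outside the SAF depend on non-serious AEs, which the plan does not provide for collecting systematically in these patients. Those categories could read as falsely low. The other five are sound under either rule.

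This rests on two readings: that the group outside the SAF consists of the no-lesion patients, who are not enrolled, and that the specific exception in Protocol 9.2.2 takes precedence over the general recording rules. If the second reading fails, the contradiction remains and only the text to be corrected changes.

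The consequence is limited to interpretation of one descriptive, unpooled table. No bias in SAF rates and no effect on the primary endpoint is shown. The wording on first-scan-only patients and the gap in Protocol 6.6.1 are matters for clarification, with no shown effect on the analysis.

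**What to change.** Choose one collection rule for gadoterate-only patients outside the SAF and match the table to it.

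- **Option (i), record all AEs.** Collect them through the 24-hour call already required. Remove the SAE-only wording from Protocol 5.1, Protocol 9.2.2 and SAP 3.1. Keep the full 11-category table, separate from the SAF table. Cost: wording, plus some extra AE entry from an existing contact.
- **Option (ii), keep the SAE-only rule.** Limit the summary to the 5 serious or fatal categories. List any non-serious AEs that were recorded, so that nothing is discarded, and footnote that they were not systematically collected. SAP 6.4.2.1 already plans listings of all AEs but does not say whether they extend beyond the SAF; state that they do. Cross-reference the exception in Protocol 10.4.1.3, 9.2.5 and 9.2.2 item 5. Cost: wording, one table shell with 6 categories removed, a listing and a footnote.

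Optional clarification: limit the first-scan-only sentence in Protocol 5.1 and SAP 3.1 to patients with no enhancing lesion, and give enrolled patients who stop after gadoterate because of an AE a class in Protocol 6.6.1, consistent with their SAF membership under SAP 4.2 and SAP 5. Cost: wording only.
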